6.4. Missing Data

For the primary analysis of the co-primary endpoints and for all CFB analyses, no imputation of missing data will be performed as the MMRM model accounts for this.

A sensitivity analysis of the co-primary endpoints will be performed using multiple imputation (MI) for missing data and is detailed in [Section 8.1.1.2](#), as well as last observation carried forward (LOCF). For all responder analyses, multiple imputation will be used to impute missing data.

Incomplete/missing start and stop dates will be handled as follows:

Incomplete AE/Concomitant Medication Start Date

If only the start day is missing, then the start day will be imputed as the first day of the month that the event occurred with the following exceptions: (1) if the partial date is the same month and year as the date of first dose of run-in single-blind medication (or double-blind medication), then the partial date will be imputed as the date of first dose of single-blind medication (or double-blind medication). However, if the date of first dose of single-blind medication and date of first dose of double-blind medication occur in the same month, then the date of first dose of double-blind medication will be imputed. (2) if the partial date is before the date of first dose of run-in single-blind medication, then the start date will be sent as the date of informed consent.

If the start date is missing both the day and month, then the day and month will be imputed as the first day of the year (i.e., 01-Jan) with the following exceptions: if the partial date is in the same year as the first dose dose of run-in single-blind medication (or double-blind medication), then the partial date will be imputed as the date of first dose of single-blind medication (or double-blind medication). However, if the date of first dose of single-blind medication and date of first dose of double-blind medication occur in the same month, then the date of first dose of double-blind medication will be imputed. (2) if the start year is before the year of first dose of run-in single-blind medication, then the start date will be sent as the date of informed consent.

Incomplete AE/Concomitant Medication or Treatment End Date

If only the end day is missing, then the end day will be imputed as the last day (28/29/30/31) of the month of occurrence. If the patient died in the same month, then set the imputed date as the death date.

If the day and month are missing, then the end day will be imputed as the 31st of December of year occurrence. If the patient died in the same year, then set the imputed date as the death date.

Missing Wake/Bed Time

For a patient with a complete diary day, if the wake and/or bed time is missing for that day then the missing time will be imputed as the average of the other wake and/or bed times from that diary. E.g., for the Week 12 diary, if the patient has 4 complete diary days with 4 wake times, but only 3 bed times of 10:00pm, 10:10pm, and 10:20pm, then the missing bed time will be imputed as the average of the observed data which is 10:10pm.

Other Data

For all other data, all available data will be included in the analyses and will be summarized as far as possible. Unless otherwise specified, there will be no substitution of missing data, i.e., missing data will not be replaced; missing data will be handled as ‘missing’ in the statistical evaluation.

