7.5.1. Prior Medication

Prior medications will be defined as medications documented on the Prior and Concomitant Medications eCRF as having stopped prior to the Run-in Visit.

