7.5.2. Concomitant Medication

Concomitant medications will be summarized separately for the Run-in Period and Double-Blind Period. Concomitant medications will be defined as taken during the Run-in Period if medications were started on or after the first dose of single-blind medication but prior to the first dose of the double-blind medication, or started prior to the first dose of the single-blind medication and were continuing to be taken during the Run-in Period. Concomitant medications will be defined as taken during the double-blind period if medications were started on or after the first dose of double-blind medication but prior to the last dose of the double-blind medication, or started prior to double-blind medication and were ongoing during the Double-Blind Period. Partial medication start dates will be imputed as detailed in [Section 6.4](#).

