9.3. Adverse Events

AEs will be coded using MedDRA version 20.0 or later.

All reported AEs (whether treatment emergent or not) will be included in by-patient AE listings. The AE listing will have a column indicating if the onset of the AE by period. Sorting will be by country, site, patient, date of event, SOC, PT and then verbatim description.

An adverse event is any untoward medical occurrence in a patient or clinical investigation patient, temporally associated with the use of a medicinal product, whether or not considered related to the medicinal product.

An AE will be considered treatment emergent (TEAE) if it begins or worsens in severity after the first dose of the double-blind Study Treatment through 28 days after the last dose of Study Treatment, or the date of initiation of another investigational agent or surgical intervention or rollover to the extension study, whichever occurs first. Partial AE start dates will be imputed as detailed in [Section 6.4](#).

A Serious Adverse Event (SAE) is any untoward medical occurrence that:

- Results in death
- Is life-threatening
- Requires inpatient hospitalization or prolongation of existing hospitalization
- Results in persistent or significant disability/incapacity
- Is a congenital anomaly/birth defect
- Is another medically important condition

In addition, any illnesses reported before starting active treatment or AE meeting the criteria of seriousness (as defined above) and considered to be possibly related (according to the Investigator) to any study-specific procedure (e.g., laboratory testing procedure, liver biopsy) must be reported as an SAE.

Summary tables will be based on treatment emergent adverse events (TEAEs). The incidence of TEAEs will be presented using counts and percentages of patients with TEAEs and tabulated by SOC and PT. SOC will be sorted in descending frequency and PT within SOC will be sorted by descending frequency based on the incidence across patients overall. If a patient has multiple occurrences (start and stop) of an event associated with a specific SOC or PT within a SOC, a patient will only be counted once in the incidence count for the SOC or PT within SOC respectively.

An overall summary table of AEs by treatment group will be presented detailing the number and percentage of patients, and number of events for the following categories:

- At least one TEAE;
- At least one Treatment-Related TEAE;
- At least one Grade ≥ 3 TEAE;

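### Section 6.4 moves partial start dates to a first-dose date without checking a known end date, so a record that ended in Run-in can be placed in the double-blind period

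*SAP*

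**What the plan says.** Section 6.4 has one set of start-date rules for adverse events and concomitant medications.

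- **Day missing.** The trigger is "if the partial date is the same month and year as the date of first dose of run-in single-blind medication (or double-blind medication"), and the result is "then the partial date will be imputed as the date of first dose of single-blind medication (or double-blind medication"). If both first doses fall in the same month, "then the date of first dose of double-blind medication will be imputed". A partial date before the first single-blind dose goes to the informed consent date.
- **Day and month missing.** The rule has the same structure, triggered "if the partial date is in the same year as the first dose dose of run-in single-blind medication" (or of the double-blind medication), with the same tie-break when both doses share a month.
- **End dates.** If the day is missing, "then the end day will be imputed as the last day (28/29/30/31) of the month of occurrence". The only bound on an imputed end date is a death date.

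Section 5.4 says that partial dates are imputed in safety data in order to assign records to study periods. Section 9.3 applies this to treatment-emergent status ("Partial AE start dates will be imputed as detailed in" Section 6.4). It also flags onset in the listing as Treatment if it is on or after the first double-blind dose. Section 7.5.2 sends partial medication start dates to 6.4 as well. Its first test for the double-blind period is whether "medications were started on or after the first dose of double-blind medication but prior to the last dose" of that medication; that test has no stop-date condition. Section 7.5.1 defines prior medications by stop date, "as having stopped prior to the Run-in Visit".

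**The concern.** The rule can contradict recorded data. If the onset day is unknown but the end date is known and precedes the first double-blind dose, the record cannot have begun on double-blind treatment. Section 6.4 nevertheless gives it an onset on the day of that dose, after its own end.

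Adverse events are collected from informed consent (Section 3.11), so such records can exist. Because the imputed date decides the period, a resolved Run-in event can move from the Run-in flag to the Treatment flag and into the treatment-emergent tables. A Run-in hypertension event could enter the hypertension table in 9.3 and drop out of the pre-double-blind hypertension listing. A serious Run-in event could leave the listing of non-treatment-emergent serious events.

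**Working it through.** The plan states no figure on this point, so the check applies the 6.4 wording to dated records.

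**Inputs**
- Run-in 01SEP2018 and Baseline 14SEP2018, the example in Section 6.5. First doses are taken to be on those days, since Section 3.11 has witnessed doses at both visits.
- For doses in different months, assumed dates of 28AUG2018 and 11SEP2018.
- Where the doses fall in different months, a partial start in the double-blind month is read as going to the double-blind date, and one in the single-blind month as going to the single-blind date.
- The end dates below are illustrative.

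**Rule as written.** Gap = imputed start minus known end.

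| Case | First doses | Recorded start | Known end | Imputed start | Gap | Onset flag |
|---|---|---|---|---|---|---|
| A | 01SEP / 14SEP | --SEP2018 | 08SEP2018 | 14SEP2018 | 14 − 8 = 6 days | Treatment |
| B | 01SEP / 14SEP | 2018 only | 20AUG2018 | 14SEP2018 | 11 + 14 = 25 days | Treatment |
| C | 28AUG / 11SEP | --SEP2018 | 05SEP2018 | 11SEP2018 | 11 − 5 = 6 days | Treatment |
| D | 28AUG / 11SEP | --AUG2018 | 03SEP2018 | 28AUG2018 | start precedes end | Run-in |
| E | 28AUG / 11SEP | 2018 only | any | not determined | – | – |

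A, B and C have an onset after their own end and fall in the wrong period. D is correct. In E, 6.4 does not say which first-dose date applies. A start month before the single-blind month goes to the consent date and is unaffected.

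**Treatment-emergent status.** The definition in 9.3 requires onset or worsening after the first double-blind dose, while the listing flag says on or after. A start imputed to the dosing day meets the flag. Under the definition, a date without a time cannot show that onset came before the dose. So A to C can be counted as treatment-emergent, and nothing in 9.3 removes them.

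**Medication with the dates of case A.** It stopped on 08SEP2018, after the Run-in Visit, so it is not prior under 7.5.1. With an imputed start of 14SEP2018:
- the Run-in tests in 7.5.2 fail, because the start is neither before the first double-blind dose nor before the first single-blind dose;
- the start-date test for the double-blind period is met.

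The record moves from the Run-in summary to the double-blind summary.

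**With an end-date check** (start = earlier of imputed start and end date): A becomes 08SEP2018, Run-in; B becomes 20AUG2018, before Run-in; C becomes 05SEP2018, Run-in. D is unchanged.

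**The case against.** The strongest defence is that defaulting a partial date to on-treatment is a deliberate conservative choice, in line with 9.3 counting missing relationship as related. That stands where the end date is unknown or falls on or after the first double-blind dose. It does not cover a record whose own end date excludes on-treatment onset.

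It can also be said that this is an edge case. It needs an unknown onset day, an end date before the first double-blind dose, and a matching month or year. Listings show missing date parts as dashes (Section 12.2.5.3), so a reader could spot such a record. That limits the size; the tables would still be wrong.

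A reader might infer more than the SAP supports:
- **Per-protocol sets.** Sections 5.6 and 5.8 settle exclusions at deviation review before unblinding. Nothing says imputed dates feed that review.
- **Washed-out drugs counted as both prior and concomitant.** Section 7.5.1 already classes a drug stopped before the Run-in Visit as prior. A double count would need prior drugs to be passed through 7.5.2 as well, which the SAP does not say.
- **Negative durations.** The SAP plans no summary of adverse event or medication duration.
- **Diluted treatment differences.** Safety data get no inferential testing (Section 9), and no rate of affected records is given.
- **A frequency from the calendar.** With a 14-day Run-in, both first doses share a month for (365 − 12 × 14)/365 = 197/365 = 54% of Run-in start dates. That is a share of calendar dates, not of affected records, and case C shows that sharing a month is not required.
- **Every year-only record.** When the doses fall in different months, the result is undetermined, as in case E.

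**Conclusion.** The point holds within limits. Section 6.4 can give an adverse event or medication a start after its known end and so place it in the double-blind period, and nothing elsewhere in the SAP corrects this. It happens:

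- when the partial start is in the month of the first double-blind dose, whether or not the single-blind dose is in that month; and
- for year-only starts when both first doses share a month.

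The effect is confined to descriptive safety and medication tables and listings; the efficacy tests are untouched. Its size cannot be computed and may be small, because the SAP gives no rate of partial dates. The conclusion rests on a literal reading of 6.4 and on the end date being known, or imputed, to precede the first double-blind dose.

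**What to change.** Add to Section 6.4:

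- If the known or imputed end date is before the first double-blind dose, the adverse event is not treatment-emergent and the medication is not double-blind concomitant.
- An imputed start date may not fall after the end date; use the earlier of the two.

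All other partial starts keep the existing default. For example, a record with both start and end given only as --SEP2018 has an imputed end of 30SEP2018, after 14SEP2018, so it still goes to the double-blind date.

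The cost is a short text addition and one extra comparison in the date-imputation code, made before unblinding. No further data are needed.

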7.2. Demographic Characteristics

All demographic and baseline characteristic data will be summarized by treatment group using descriptive statistics for all patients for each of the following analysis sets: SAF, FAS, FAS-I, PPS and PPS-I.

Sex, Region (US and non-US), OAB Type (OAB Wet and OAB Dry), OAB-d Type (OAB Wet, OAB Dry and Missing), Prior Anticholinergic Use in the Last 12 Months (Yes/No), Prior Beta-3 agonist Use in the Last 12 Months (Yes/No), Benign Prostatic Hyperplasia (BPH) (males only: Yes/No), Diabetes Mellitus (Yes/No), Baseline Hypertension (Yes/No), Pre-existing Hypertension (Yes/No), Child-bearing Potential (females only: Yes/No), Age category 1 (<40, ≥40 to <55, ≥55 to <65, ≥65 to <75, ≥75 years), Age

category 2 (<65, ≥65 years), Age category 3 (18 to <65, ≥65 to <85 years, ≥85 years), Ethnicity and Race (white and other) will be summarized by the number and percentage of patients in each category.

Prior Anticholinergic Use in the Last 12 Months and Prior Beta-3 agonist Use in the Last 12 Months are considered prior medications and will be defined as medications documented on the Prior and Concomitant Medications eCRF as having stopped prior to the Run-in Visit.

Baseline Hypertension will be defined as baseline systolic blood pressure (SBP) ≥140 mmHg or baseline diastolic blood pressure (DBP) ≥90 mmHg, regardless of medical history.

Pre-existing hypertension will be defined as having a medical history of hypertension or Baseline hypertension (baseline SBP ≥140 mmHg or baseline DBP ≥90 mmHg).

Age (years), height (cm), weight (kg) and BMI captured at Screening will be summarized as a continuous variable.

Unless otherwise stated, percentages will be calculated out of the number of patients in the given Analysis Set.

All demographic data will be listed.

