7.5.3. Other Therapies

Prior OAB medication will be recorded at screening visit. The following criterion will be used for selecting prior OAB medication:

Table 7.5.3: OAB Medication Selection

Class	Variable Selected	Selection
Anticholinergics	Preferred Term	darifenacin, fesoterodine, festoterodine fumarate hyoscyamine, oxybutynin, oxybutynin hydrochloride, propantheline, solifenacin, solifenacin succinate, tolterodine, tolterodine l-tartrate, trospium, and trospium chloride
Beta-3 adrenergic agonists	Preferred Term	Mirabegron, vibegron

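### SAP 7.2 bases the 12-month prior anticholinergic and beta-3 flags on a stop before Run-in, so some recent users, including those with year-only stop dates, are coded No

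*SAP*

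**What the plan says.** - **Section 6.4**, under "Incomplete AE/Concomitant Medication or Treatment End Date", covers medications as well as adverse events. For a date with only the year known it says: "If the day and month are missing, then the end day will be imputed as the 31st of December of year occurrence". The one exception is death: "If the patient died in the same year, then set the imputed date as the death date". Nothing caps the imputed date at Run-in, first dose or last visit.
- **Section 7.2** derives both 12-month prior-use flags from "medications documented on the Prior and Concomitant Medications eCRF as having stopped prior to the Run-in Visit". Section 7.5.1 uses the same test for prior medication in general.
- **Section 7.5.2** treats as double-blind concomitant any drug "started prior to double-blind medication and were ongoing during the Double-Blind Period". It refers to 6.4 only for partial start dates.
- **Section 7.5.3** selects prior OAB medication by Preferred Term and states no stop-date test. Its anticholinergic list has the base spelled fesoterodine and the salt spelled "festoterodine fumarate".
- **Section 3.11, footnote 16** has OAB medications from the year before Screening recorded for every patient.
- **Sections 6.7 and 8.1.4** name both flags as subgroups for the co-primary endpoints and restrict them to descriptive statistics.

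**The concern.** The flag's label asks whether a drug was used in the last 12 months. Its derivation asks whether the drug had stopped by Run-in. The two answers differ for two kinds of patient, and in both a user is coded No.

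1. The drug stopped in the run-in year but only the year was recorded. Section 6.4 moves the stop to 31 December, normally after Run-in, and the drug no longer counts as prior.
2. The drug was not stopped before Run-in. No imputation is involved, yet a current user is coded as having no use in the past year.

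The flags describe the population in five analysis sets (SAF, FAS, FAS-I, PPS, PPS-I) and define subgroup summaries of both co-primary endpoints. Users placed in the No group blur the contrast between previously treated and untreated patients. That contrast is of some interest in a trial with an anticholinergic as active control. The prior OAB medication table, selected by drug name, could also show a drug for a patient whose baseline flag says No.

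**Working it through.** The SAP gives no figure on this point, so there is none to reproduce. The check applies its date rules directly.

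**Inputs**
- Year-only stop date: 31 December of the stop year (6.4).
- Prior: stop before the Run-in Visit (7.2).
- Timing: Screening at Day -49, Run-in at Day -14, Day 1 at Baseline, no Day 0 (3.11, 6.3). A drug stopped at Screening for washout therefore stops 49 - 14 = 35 days before Run-in and 49 days before Day 1.
- Assumption: a 365-day year, with every calendar stop date considered once.

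**One patient, using the example visits in 6.5** (Run-in 01SEP2018, Baseline 14SEP2018). A drug stopped 35 days before Run-in stopped on 28JUL2018. Recorded only as 2018, it becomes 31DEC2018. Week 12 falls at 14SEP2018 + 84 days = 07DEC2018. The imputed stop is later than Run-in, Day 1 and Week 12, so the drug is not prior and the flag is No unless another record of that class stopped before Run-in.

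**All stop dates.** For a stop on day *d* of the year and Run-in *g* days later, the imputed date is on or after Run-in when *d* + *g* ≤ 365. That holds for 365 - *g* of the 365 dates.

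| Gap *g* from stop to Run-in | Dates coded not prior | Share |
|---|---|---|
| 32 days | 333 | 91% |
| 35 days | 330 | 90% |
| 38 days | 327 | 90% |
| 60 days | 305 | 84% |
| 90 days | 275 | 75% |
| 180 days | 185 | 51% |
| 270 days | 95 | 26% |
| 365 days | 0 | 0% |

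At the 35-day gap, stops from 27 November onward put Run-in in the next calendar year and stay correctly prior (35 dates). Using Day 1 in place of Run-in, 365 - 49 = 316 dates (87%) also make the drug double-blind concomitant.

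**Only the day missing.** Month-end imputation moves a date by at most 30 days, less than 35, so 0 of 365 dates flip at that gap. At the washout gap the imputation fault is specific to year-only stop dates.

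**Spelling.** An exact match on "festoterodine fumarate" would not find a record coded to the correctly spelled fumarate. A record coded to the base would still be found. The misspelling directly affects the prior OAB medication table. It affects the flag only if the flag uses Table 7.5.3: Section 7.2 names no list, and 6.7 points to a protocol table for the anticholinergics.

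**The case against.** **The definition can be read as the recorded entry.** Section 7.2 speaks of what the eCRF documents, the 6.4 heading does not name prior medication, and 7.5.2 invokes 6.4 for start dates only. The ambiguity is real, but it does not rescue the flag. An entry giving only the run-in year cannot by itself show a stop before Run-in. A separate stopped-before-Run-in item on the eCRF could, but the SAP describes none.

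**The case is rare.** A drug stopped for washout is stopped within the study's own Screening period, with medications reviewed at each visit, so a year-only date there is unlikely. Vaguer dates are likelier for older stops, and those in the previous calendar year stay correctly prior. A patient also flips only without another qualifying record of the class. All of this stands and limits the size. A drug not stopped before Run-in should also be uncommon, given the planned washout.

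**Latest-date imputation is a defensible convention.** It avoids missing exposure on treatment. This stands for the concomitant medication tables, and the 31 December rule can remain there.

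**Stronger readings.** A reader might infer that washed-out drugs will appear as prohibited on-treatment use and remove patients from the Per-Protocol Sets. The SAP does not support that: Sections 5.6 and 5.8 leave those exclusions to documented review before unblinding, not to an imputed date. A reader might also infer that subgroup inference on the co-primary endpoints is compromised. Section 8.1.4 fits no model for these two subgroups.

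**Conclusion.** The point holds as a fault in how the two flags are defined. As written, a recent user is coded No when a listed drug stopped in the run-in year with a year-only stop date and no other record of the class qualifies, or when the drug was not stopped before Run-in. In these cases the error always moves users into the No group.

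The 90% is a share of calendar stop dates, conditional on a year-only entry and a 35-day gap. It is not a share of patients. The frequency of such entries is not given, so the number affected cannot be estimated and is probably small.

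The reach is the baseline tables and the descriptive subgroup summaries. Neither flag is a stratification factor (3.9) or a term in the primary model (8.1.1.1), and no co-primary or key secondary test changes. The misspelled term is a minor error of the same kind, with an effect only under exact matching. This is worth correcting because correction is nearly free, not because a main conclusion depends on it.

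**What to change.** 1. **Section 7.2:** define each flag as any record of a Table 7.5.3 drug of that class taken within 12 months before Screening, regardless of its recorded or imputed stop date. The data are already collected under footnote 16 of Section 3.11. Name Table 7.5.3 as the list.
2. **Section 6.4:** keep the 31 December rule for the concomitant medication tables and add that imputed end dates do not determine the prior-use flags. Imputed start dates should not decide them either, since 6.4 moves a year-only start in the run-in year to the first dose of study medication.
3. **Table 7.5.3:** correct the misspelled term and select all salts of each listed drug.

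Because the flag no longer tests the stop date, the 330 of 365 misclassified dates at the 35-day gap fall to 0. The cost is a few lines of SAP wording and code before unblinding, with no new data. An alternative is to cap the imputed stop for drugs marked as stopped before Run-in, but that relies on an eCRF item the SAP does not describe, so redefining the flag is safer.
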